8.2.1. Inclusion criteria

Patients must meet all of the following inclusion criteria to be eligible for inclusion in the study:

1. Unique enrollees in the HealthVerity Vaccine dataset any time **after** 10 December 2020
2. At least 12 years on the index date (ie, first vaccination date)
3. No evidence of prior COVID-19 infection (a medical claim, pharmacy claim, or chargemaster record with an International Classification of Diseases, 10th Revision, Clinical Modification (ICD-10-CM) diagnosis code of U07.1) in the 12 months prior to the index date
4. Have 12 months of continuous enrollment with medical benefits (with or without pharmacy benefits) prior to the index date

Subjects with an IC condition were identified via an algorithm originally developed and validated by Greenberg et al²⁴ for use in administrative claims database studies. For this study, this algorithm will be modified and expanded based on expert medical opinion. The algorithm is depicted in [Figure 1](#).

Subjects will be identified as immunocompromised if they had ≥ 1 hospitalization or ≥ 2 outpatient visits on separate dates with an ICD-10-CM code on a healthcare claim indicating an IC condition or if they had usage of specific immunosuppressive medications during the 12-month baseline period. The IC case definition will incorporate 8 groups based on clinical diagnoses only, 1 group based on both clinical diagnoses and usage of immunosuppressive medication, and 2 other groups based on usage of immunosuppressive medication only, for a total of 11 groups with an IC condition ([Figure 1](#)). Subjects with >1 IC condition will also be assessed, for a total of 12 mutually exclusive groups for inclusion in this study. The list of ICD-10-CM codes used to identify IC cases by diagnosis and list of immunosuppressive medications are shown in the Annex.

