Eight of the disease groups will include subjects with 1) symptomatic human immunodeficiency virus (HIV)/acquired immunodeficiency syndrome (AIDS); 2) solid malignancy; 3) bone marrow transplant; 4) organ transplant (excluding bone marrow); 5) rheumatologic or other inflammatory condition; 6) a primary immunodeficiency; 7) other immune conditions; and 8) chronic kidney disease (CKD) or end stage renal disease (ESRD). Subjects in these IC groups (shown as “Group 1” in [Figure 1](#)) will be further stratified by treatment status: those with usage of immunosuppressive medications for >14 days anytime during the baseline period and those without any evidence of >14 days of usage of an immunosuppressive medication during the baseline period. Subjects with a bone marrow or

organ transplant will be further stratified by those who received their 1st vaccine dose >100 days prior to their transplant and those who received it <100 days prior to their transplant. Subjects with a solid malignancy will be further stratified by their treatment type: chemotherapy or radiation therapy or immunomodulator, or a mix of these treatments.

The 9th subject group (shown as “Group 2” in [Figure 1](#)) will include those with a hematologic malignancy, required to have usage of an immunosuppressive medication (chemotherapeutic agent, immunomodulator, or systemic corticosteroid) for >14 days anytime during the baseline period; this subject group will be further stratified by their use of an immunosuppressive medication >6 months or ≤ 6 months prior to their index date.

The 10th subject group will include subjects with usage of an immunosuppressive medication (chemotherapeutic agent, immunomodulator, or systemic corticosteroid excluding low-dose [<60mg/day] prednisone) for >14 days anytime during the baseline period, but without any ICD-10-CM diagnosis codes indicating the above listed IC conditions on a healthcare claim anytime during the baseline period. Subjects with >14 days usage of antimetabolites anytime during the baseline period will be excluded from this subject group and placed in the 11th subject group.

[figure not shown]

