8.3. Variables

Table 1. Immunocompromising Conditions definition

Variable	Role	Data source(s)	Operational definition
Immunocompromising Conditions	Cohort Definition	HealthVerity Vaccine Data	
Subjects will be categorized into the following 12 mutually exclusive IC groups based on the algorithm detailed in Figure 1:
 
Symptomatic HIV/AIDS, solid malignancy, bone marrow transplant recipients, organ transplant recipients, rheumatologic or other inflammatory conditions, primary immunodeficiencies, other intrinsic immune conditions, chronic kidney disease or end stage renal disease, hematologic malignancy, immunosuppressive treatment only, antimetabolites only, or >1 IC condition.

PFIZER CONFIDENTIAL

Table 1. Immunocompromising Conditions definition

Variable	Role	Data source(s)	Operational definition
			
Subjects falling into more than one of these categories will be categorized as having >1 IC condition.
 
At a minimum, subjects will be required to have one inpatient claim or two outpatient claims on separate days with the IC condition of interest in the baseline period. In cases when >14 days of treatment are required it will be based on the dispensed day supply or distinct days of treatment in the baseline period.
 
The main diagnosis codes to identify IC conditions are presented in ANNEX 1. LIST OF STAND ALONE DOCUMENTS.

Table 2. Vaccination Status definitions

Variable	Role	Data source(s)	Operational definition
Any vaccination	Cohort Definition	HealthVerity Vaccine Data	
Patients with a claim for any vaccine will be considered vaccinated with any vaccine based on the following codes:
 
Pfizer/BioNTech: 91300, 0001A, 0002A, 59267100001, 59267100002, 59267100003
 
Moderna: 91301, 0011A, 0012A, 80777027310, 80777027399, 80777027315, 80777027398
 
Johnson & Johnson: 91303, 0031A, 59676058005, 59676058015
 
Source: https://www.cdc.gov/vaccines/programs/iis/COVID-19-related-codes.html

Fully Vaccinated	Cohort Definition	HealthVerity Vaccine Data	
Patients will be considered fully vaccinated if they meet any of the following definitions:
 
Two claims for Pfizer/BioNTech vaccine on separate days with >14 days of follow-up after the 2nd vaccination date. No claims for any other vaccines are allowed.

PFIZER CONFIDENTIAL

Table 2. Vaccination Status definitions

Variable	Role	Data source(s)	Operational definition

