- IS drug use: >14 days IS medications (chemotherapy, immuno-modulators (IM), or corticosteroids excluding low-dose [<60mg/day] prednisone – See Drug List) and not falling into any of the above 9 condition groups
- >14 days of anti-metabolite use and not falling into any of the above 10 condition or drug use groups
- More than 1 IC condition

PFIZER CONFIDENTIAL

Analyses for younger cohorts (eg, 12-15) will also be conducted, as data accumulates.

For the exploratory aim, the Screening Method will be used to calculate VE for the overall study population of subjects with an IC condition and also stratified VE estimates for the different immunocompromised subject groups, with VE also determined for those subjects with >1 IC condition²⁶. We will use the proportion of the population that are vaccinated (PV) and the proportion of subjects with breakthrough SARS-CoV-2 infections that are vaccinated (PCV) to calculate VE using the following formula:

$$VE = (PV - PCV) / [PV(1-PCV)]$$

where PV = the proportion of the population that is vaccinated (ie, vaccination coverage) and PCV = the proportion of subjects with breakthrough SARS-CoV-2 infections that are vaccinated.

Additionally, breakthrough incidence rates and VE will be stratified by age at diagnosis (eg, < 65 and \geq 65 years of age at index vaccination).

Sensitivity analyses will be conducted to test the robustness of findings by varying key study design aspects (eg, continuous enrolment, IC case definition) and data analysis techniques. Other statistical techniques (eg, matched analyses, multiple regression, propensity scores) may be applied on an exploratory basis after careful examination of potential confounders (eg, age, time from vaccination). Exploratory analyses related to alternate dosing may also be conducted upon feasibility results, and as recommendations from public health authorities evolve. The analyses (entirely or in part) will be conducted over time and updated on a rolling basis as monthly data cuts become available.

While the analyses will be focused on the IC population, analyses will also be conducted (in part or entirely) on the non-IC population, the total (IC + non-IC) population or relevant subgroups (eg, other high-risk conditions, vaccination status) to support the interpretation of findings.

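### As written, the drug-only group rules, the Annex 3 code list and the transplant-timing strata put some subjects in conflicting or wrong condition-specific IC groups

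*Combined protocol and SAP*

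**What the plan says.** **Drug-only groups.** Section 8.2.1 defines group 10 as more than 14 days of an immunosuppressant "but without any ICD-10-CM diagnosis codes indicating the above listed IC conditions on a healthcare claim anytime during the baseline period". Users of antimetabolites for more than 14 days "will be excluded from this subject group and placed in the 11th subject group". Section 8.7 lists the same groups for the subgroup analyses. There, group 10 is drug use "and not falling into any of the above 9 condition groups", and group 11 is ">14 days of anti-metabolite use and not falling into any of the above 10 condition or drug use groups". Table 1 in Section 8.3 names the last three groups as "immunosuppressive treatment only, antimetabolites only, or >1 IC condition" and adds: "Subjects falling into more than one of these categories will be categorized as having >1 IC condition".

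**Diagnosis groups.** Under Section 8.2.1, entry needs one hospital stay, or outpatient visits on at least two dates, with a listed code. The groups are mutually exclusive, and anyone who meets more than one goes to group 12 (more than one IC condition). Annex 3 gives the codes.

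**Transplant strata.** Section 8.2.1 splits bone marrow and organ transplant recipients by whether the first vaccine dose came more than 100, or less than 100, days before the transplant. Section 8.1 sets the baseline, in which IC conditions are identified, as the 12 months before that dose. A later paragraph of 8.2.1 describes the timing split for organ transplant without giving a direction.

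**The concern.** The condition-specific groups carry a secondary objective (Section 7) and the stratified exploratory vaccine effectiveness estimates (Section 8.7). Section 6 gives as the rationale learning which IC conditions go with reduced effectiveness. If two sections place the same subject differently, the content of a group depends on which section is programmed. If one code meets two groups, group 12 takes in subjects with a single diagnosis, and the condition groups lose them. If the transplant strata cannot be filled, a planned stratification yields nothing.

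**Working it through.** No sample size or power figure applies. The group count is right: 8 + 1 + 2 = 11, plus group 12 = 12. The rest is a check of logic.

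**(a) Groups 10 and 11.** Take drug users of more than 14 days without a qualifying diagnosis: no IC code or one outpatient code, by other immunosuppressant only, antimetabolite only, or both. That is 2 × 3 = 6 profiles. The text leaves three things open, giving 2 × 2 × 2 = 8 readings:
- A: antimetabolites count as group 10 drugs.
- B: Section 8.7 takes over the antimetabolite exclusion of 8.2.1.
- C: the no-code condition of 8.2.1 extends to group 11.

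Under 8.2.1, other-drug users are in group 10 with no code and in no group with one code. Antimetabolite users are in group 11, except that one-code subjects have no group if C holds. Under 8.7, other-drug users are in group 10 with or without the code. Antimetabolite users are in group 11 if B holds. If B does not hold, users of both are in group 10, and antimetabolite-only users are in group 10 if A holds and in group 11 if not.

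| A | B | C | Profiles placed differently (of 6) |
|---|---|---|---|
| no | no | no | 3 |
| no | no | yes | 4 |
| no | yes | no | 1 |
| no | yes | yes | 3 |
| yes | no | no | 5 |
| yes | no | yes | 5 |
| yes | yes | no | 1 |
| yes | yes | yes | 3 |

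Exactly one profile differs in all 8 rows: one outpatient code with another immunosuppressant only (no group against group 10). In the two rows showing 1, no antimetabolite user is placed differently.

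**(b) Annex 3.** Each stem was compared with the codes and ranges of every other group, reading D72 under Primary Immunodeficiency as D72.0.

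| Pair of groups | Stems | Number |
|---|---|---|
| Solid malignancy / CKD | C64, C68.9, D30.0, D41.0, D41.1, D41.2 | 6 |
| Primary Immunodeficiency / Other immune | D71, D72.89, D72.0 | 3 |
| Rheumatologic / CKD | M10.3, M32.14, M32.15 | 3 |
| Solid malignancy / Other immune | D47.4 | 1 |

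The total is 6 + 3 + 3 + 1 = 13. Two are printed identically in both groups (D71, D72.89), 3 overlap through a parent code (D72.0, M32.14, M32.15) and 8 through a range. If D72 means the category, D72.81 and D72.9 are added: 15. If D41.0 to D41.2 is counted as one entry, 13 becomes 11. A subject whose only IC diagnosis is one of these codes meets two groups and goes to group 12.

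**(c) Transplant strata.** Let t be the day of transplant, with the first dose on day 0. Read literally, one stratum needs t > 100 and the other 0 < t < 100. A transplant already coded in baseline has t < 0 and enters neither. Only a further transplant after the first dose could enter, and from the earliest index date (11 December 2020) to the stated cut (8 July 2021) there are at most 209 days. Read as a signed difference, t < 100 takes in every t < 0, so nearly all recipients fall in one stratum. On both readings t = 100 is in neither. Measured instead from transplant to dose, a transplant on day −150 falls in >100 and one on day −30 in <100, so both strata can fill; exactly 100 days is still unassigned. Annex 3 lists only status and complication codes for transplant, so the transplant date has no stated source.

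**The case against.** Section 8.2.1 is the operative definition, and the list in 8.7 only names subgroups. Read that way, antimetabolite users go to group 11 throughout. Table 1 gives labels that rest on the Figure 1 algorithm. Someone excluded from group 10 is not in two drug categories, so the rule for more than one condition is not triggered. A reader might infer that the documents state three incompatible rules for group 11. They do not: that conflict arises only if 8.7 and Table 1 are read independently of 8.2.1. The group 10 conflict remains. It would vanish only if a code indicating a condition meant one that meets the entry threshold, and the words any and anytime in 8.2.1 weigh against that.

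Sending overlaps to group 12 is a stated rule, so the groups do stay mutually exclusive. M32.14 and M32.15 sit under both lupus and kidney disease and may properly be both conditions. That does not explain D71 or D72.89, which are printed in both lists with no sign that a dual condition is meant.

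The transplant wording looks like a drafting slip, and the strata are essentially empty only on the literal reading. The signed reading still gives an uninformative split, and the neutral sentence later in 8.2.1 does not supply a direction.

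The study is mainly descriptive (Section 8.5), and sensitivity analyses on the IC case definition are planned (Section 8.7). This limits the consequence, but those analyses would vary a base definition that is not yet unique.

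**Conclusion.** The concern holds for the condition-specific groups and should be settled before programming. Its size can be given only in rules and codes: one drug-user profile placed differently in all 8 readings, 13 two-group stems (11 to 15 by convention), and two transplant strata that are essentially empty or, on the signed reading, nearly all in one. The documents give no patient counts. Figure 1 is not shown, so it could not be checked. It may state an order of precedence, but it would not make the written sections agree.

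A reader might go further and infer that the primary IC versus non-IC comparison is wrong. The documents do not support that. Section 8.2.1 makes a subject IC on a qualifying diagnosis "or if they had usage of specific immunosuppressive medications during the 12-month baseline period", and then says "The IC case definition will incorporate 8 groups based on clinical diagnoses only", followed by the drug-based groups. Whether the one-code drug user is an IC subject without a group or a non-IC subject depends on which sentence governs. The text does not settle this.

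**What to change.** 1. Bring Sections 8.2.1 and 8.7, Table 1 and Figure 1 to one rule: groups 10 and 11 each require that the subject is not in groups 1 to 9, and users of antimetabolites for more than 14 days go to group 11, as 8.2.1 states. Each of the six profiles then has exactly one group: other drug only in 10, antimetabolite only or both in 11.
2. Before programming, do not let a single code by itself satisfy two groups. Assign each overlapping code to one group, except those the sponsor deliberately keeps as dual conditions. State whether D72 means D72.0 or the category.
3. Reconcile the transplant strata with the baseline window, as time from transplant to first dose. Assign exactly 100 days to one stratum and report undated transplants separately.
4. Reconcile the drug-use sentence in 8.2.1 with the group entry rules. The IC cohort need not be redefined for this.

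The cost is minor protocol wording and code-map work. Some transplant recipients will remain undated; how many cannot be derived from the documents.

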8. RESEARCH METHODS

8.1. Study design

This study will be a retrospective database analysis utilizing data sets within the HealthVerity database (Philadelphia, Pennsylvania) covering the time period 01 December 2018 through 08 July 2021 (or latest data available) to describe the characteristics of subjects with IC conditions vaccinated with BNT162b2 and to evaluate the incidence of SARS-CoV-2 breakthrough infections.

Study period: 01 December 2018 – 08 July 2021 (or latest data available)

Index identification period: 11 December 2020 – 08 July 2021 (or latest data available; inclusive)

Index date: The first record for a SARS-CoV-2 vaccine (primary analysis: BNT162b2; sensitivity analyses: any Mrna, any authorized vaccine) from a medical claim, pharmacy claim, or chargemaster record.

Baseline period: 12-month period prior to the index vaccination date

Follow-up period: Variable period beginning after the index date and continuing until the earliest of the following: end of the study or end of continuous insurance enrollment.

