This algorithm differs from that used in Greenberg et al²⁶ by the following modifications, considered relevant for COVID-19 based on expert medical opinion: the inclusion of subjects with a solid malignancy who had radiation therapy or any treatment mix; the separation of subjects with a bone marrow transplant and those with an organ transplant; the inclusion of chronic inflammatory demyelinating polyneuropathy and immune thrombocytopenic purpura in the “rheumatologic or other inflammatory condition” group; the inclusion of sickle cell disease, asplenia, and psoriatic arthritis in the “other immune disorders” group; the addition of subjects with primary immunodeficiencies and those with CKD or ESRD; the requirement that subjects with a hematologic malignancy have evidence of usage of an immunosuppressive medication; the reclassification of subjects with only usage of an immunosuppressive medication; the removal of subjects with usage of only low dose prednisone; and the inclusion of an ad-hoc group of subjects who had taken anti-metabolites. Additionally, the following subcategories will be created: the first 9 subject groups were stratified according to treatment status; organ transplant subjects will be stratified according to time of receipt of the first COVID-19 vaccine dose in relation to the date of transplant; and subjects with hematologic malignancy will be stratified by time of receipt of treatment relative to their 1st vaccine dose.

When categorizing subjects with the different types of IC conditions, all the subject groups will be mutually exclusive. Subjects meeting the criteria for classification into only a single IC group will be classified accordingly into subject groups 1-11. Any subjects meeting the criteria for classification into multiple IC groups will be categorized into the >1 IC condition group (12th subject group).

All subjects will be grouped into an overall study population consisting of subjects identified as having an IC condition or not (i.e., non-IC). Subjects with an IC condition will be further categorized into the specific IC condition groups.

Figure 1: Algorithm to define immunocompromising conditions

Algorithm for case definitions of IC conditions in HealthVerity US claims database

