US Geographic Region	Patient Characteristics	HealthVerity Vaccine Data	
US geographic region will be derived from the patient state and categorized into the following:
 
Northeast – Connecticut, Maine, Massachusetts, New Hampshire, Rhode Island, Vermont, New Jersey, New York, Pennsylvania
 
Midwest – Indiana, Illinois, Michigan, Ohio, Wisconsin, Iowa, Kansas, Minnesota, Missouri, Nebraska, North Dakota, South Dakota
 
South – Delaware, District of Columbia, Florida, Georgia, Maryland, North Carolina, South Carolina, Virginia, West Virginia, Alabama, Kentucky, Mississippi, Tennessee, Arkansas, Louisiana, Oklahoma, Texas
 
West – Arizona, Colorado, Idaho, New Mexico, Montana, Utah, Nevada, Wyoming, Alaska, California, Hawaii, Oregon, Washington
 
Other – Puerto Rico

Payer/insurance coverage on index date	Patient characteristics	HealthVerity Vaccine Data	Payer on index date will be reported as the following categories: Commercial, Medicaid, Medicare, Unknown, or missing. If multiple payers are reported on the index date, those will be captured under an ad-hoc "Multiple" category.
Vaccine Administration Setting	Patient characteristics	HealthVerity Vaccine Data	Vaccine administration setting will be determined based on the reported place of service for the claim. Prescription claims will be assumed to have occurred in the Pharmacy setting. The most common settings will be reported.
Conditions that place or may place patients at risk of Severe COVID-19 (6 months prior)	Patient Characteristics	HealthVerity Vaccine Data	Baseline comorbid conditions that place or may place patients at risk of Severe COVID-19 infection will be assessed in the 6 months prior to index vaccination. The ICD-10-CM, ICD-10 Procedure Coding System (ICD-10-

PFIZER CONFIDENTIAL

Table 3. Patient Characteristics and Vaccine Utilization variable definitions

Variable	Role	Data source(s)	Operational definition
			PCS), Current Procedural Terminology (CPT-4), and Healthcare Common Procedure Coding System (HCPCS) codes used to identify these conditions are based on the Sentinel COVID-19 Natural History Master Protocol (https://www.sentinelinitiative.org/methods-data-tools/methods/master-protocol-development-covid-19-natural-history)

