ANNEX 3. ICD-10 CODE LIST

IC Condition	ICD-10 Code
HIV/AIDS*	B20-B24
Solid malignancy	
Organ/system malignant tumors	C00-C07; C11-C19; C22-C80; Z85
Neuroendocrine tumors	C7A; C7B; D3A
Neoplasms of uncertain behavior	D00-D49
Bone marrow transplant	Z94.81
Organ transplant	
Complications of transplanted organ	T86
Organ transplant status	Z94 except Z94.81; Z98.85
Rheumatologic or other inflammatory condition	
Sarcoidosis	D86
Amyloidosis Not Otherwise Specified (NOS)	E85
Familial Mediterranean fever	E85.0; M04
Amyloidosis Not Elsewhere Classified (NEC)	E85.1; E85.3; E85.8
Multiple sclerosis	G35
Other Central Nervous System (CNS) demyelination	G36; G37.1; G37.3; G37.8; G37.9
Acute infective polyneuritis	G61.0; G61.9
Acute myocarditis	I40
Polyarteritis nodosa and other	M30
Allergic alveolitis/pneumonitis NOS	T78.40; J67.9
Other alveolar pneumonopathy	J84.01; J84.02; J84.09

PFIZER CONFIDENTIAL

IC Condition	ICD-10 Code
Enteritis and colitis	K50-K52
Lupus erythematosus	L93.0; L93.2; M32
Diffuse connective tissue disease	L94; M35.8; M35.9
Arthropathy with infection	M12.9; M01.X0; M02.10
Crystal arthropathies	M11
Rheumatoid arthritis/inflammatory polyarthropathy	M05-M14
Inflammatory spondylopathies	M46
Polymyalgia rheumatica	M31.5; M35.3
Chronic inflammatory demyelinating polyneuropathy	G61.81
Immune thrombocytopenic purpura	D69.3
Primary Immunodeficiency	
X-linked agammaglobulinemia	D80.8
Common variable immunodeficiency	D83.1; D83.2; D83.8; D83.9
Immunoglobulin A (IgA) deficiency	D80.2
Immunoglobulin G (IgG) sub-class deficiency	D80.3
Severe combined immunodeficiency	D81.1
Di George syndrome	D82.1
Wiskott-Aldrich	D82.0
Ataxia telangiectasia	G11.3
Interferon-gamma/Interleukin 12 axis deficiencies	D84.89
Persistent complement, properdin or Factor B deficiency	D84.1
Received eculizumab for >14 days in the baseline period	
Chronic granulomatous disease	D71
Chediak-Higashi	E70.330
Leukocyte adhesion deficiency	D72: Genetic anomalies of leukocytes
Myeloperoxidase deficiency	D72.89: Other specific disorders of White Blood Cells (WBCs)

PFIZER CONFIDENTIAL

IC Condition	ICD-10 Code
Other immune conditions	
Disorders of immune mechanism	D89
Neutropenia	D70
Functional disorders of neutrophils	D71
Genetic anomalies of leukocytes	D72.0
Decreased leukocyte count	D72.81
Leukocyte disease NEC	D72.89
Leukocyte disease NOS	D72.9
Myelofibrosis	D75.81
Blood diseases NEC	D47.4; D75.89; D75.9; D89.2
Blood diseases NOS	D75.9; D75.89
Immunologic findings NEC	R76; R83.4-R87.4; R89.4

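### The 100-day transplant strata have no defined transplant date: Annex 3 lists only status and complication codes, so long-standing recipients may be mixed into the stratum nearest transplant to an unknown extent

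*Combined protocol and SAP*

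**What the plan says.** Section 8.2.1 divides transplant recipients by timing. The detailed paragraph covers bone marrow as well as organ recipients: those with a bone marrow or "organ transplant will be further stratified by those who received their 1st vaccine dose >100 days prior to their transplant", against those with fewer than 100 days. The later summary of changes to the algorithm says only that "organ transplant subjects will be stratified according to time of receipt of the first COVID-19 vaccine dose in relation to the date of transplant".

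Annex 3 gives these codes for the two groups:

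- Bone marrow transplant: Z94.81 alone.
- Organ transplant: T86, labelled "Complications of transplanted organ", and a status row reading "Z94 except Z94.81; Z98.85".

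Table 1 (section 8.3) sets the entry rule as "one inpatient claim or two outpatient claims on separate days with the IC condition of interest in the baseline period". Section 8.1 gives "Baseline period: 12-month period prior to the index vaccination date". No readable section says which record supplies the transplant date.

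Procedure codes are used elsewhere in the plan. The dialysis rows of Annex 3 list them, and Table 3 refers to ICD-10-PCS together with "Current Procedural Terminology (CPT-4), and Healthcare Common Procedure Coding System (HCPCS) codes used to identify these conditions".

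**The concern.** A split at 100 days needs a date for the operation. Status and complication codes can be recorded at any visit after a transplant, and the entry rule asks only for such codes within 12 months. A person transplanted many years ago therefore qualifies on the same codes as one transplanted last month. An analyst who uses only the listed codes must let a visit date stand in for the transplant date, and the protocol does not say which visit.

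Two things are at stake. The first is reproducibility: two competent analysts could build very different strata from the same text. The second is dilution. Suppose a share c of the stratum nearest transplant is really long-standing, those recipients have the other stratum's breakthrough rate, and the other stratum is clean. The observed rate difference is then (1 − c) times the true one. A difference by time since transplant could be understated or missed.

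**Working it through.** The plan gives no stratum size, visit rate or misclassification figure, so there is nothing to reproduce. The calculations below are illustrations.

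**From the documents.** Cut at 100 days; baseline 12 months (365 days used); entry by one inpatient or two outpatient coded claims; data from 01 December 2018, which is 741 days before the earliest index date (11 December 2020) and 950 days before 08 July 2021.

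**Assumed.** Long-standing recipients have coded visits as a Poisson process at L per year (2 to 12). The true share of recipients within 100 days of transplant is r (0.02 to 0.10; transplants spread evenly over ten years give 100/3650 = 0.027). All truly near recipients are placed correctly.

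**Formula.** Let q be the probability that a qualified long-standing recipient's proxy date falls in the last 100 days. The long-standing share of the near stratum is (1 − r)q / [(1 − r)q + r]. Let G(m) = 1 − e^(−m)(1 + m), the Poisson probability of at least two codes. In this step long-standing recipients qualify on two coded dates.

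- Rule A, first code in the 365-day baseline: q = e^(−265L/365) · G(100L/365) / G(L).
- Rule B, first code in about 740 days of data: the same with 640 in place of 265.
- Rule C, latest code before index: q = 1 − e^(−100L/365) · G(265L/365) / G(L).

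Example, rule A with L = 2: q = 0.2341 × 0.1051 / 0.5940 = 0.0414. At r = 0.027 the share is 0.973 × 0.0414 / (0.973 × 0.0414 + 0.027) = 0.60.

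| Coded visits/year | A, r = 0.027 | B, r = 0.027 | C, r = 0.027 |
|---|---|---|---|
| 2 | 60% | 16% | 96% |
| 3 | 50% | 4% | 96% |
| 4 | 39% | 1% | 96% |
| 6 | 19% | about 0% | 97% |
| 12 | 0.5% | about 0% | 97% |

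Over r = 0.02 to 0.10 the ranges are 0.1–67% (A), 0–21% (B) and 84–98% (C).

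**Simulation of rule A with the inpatient route included.** Time since transplant is uniform over 5 or 10 years, with 400,000 subjects per setting. The transplant admission is assumed to carry a listed code, so it qualifies the subject by itself and dates the transplant when it falls in baseline. Coding is either dense in the first year (24 a year to day 100, then 12 a year to day 365) or constant at L throughout.

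| Coded visits/year (long term) | Dense early coding, 5 / 10 years | Constant rate, 5 / 10 years |
|---|---|---|
| 2 | 22% / 42% | 27% / 45% |
| 4 | 16% / 32% | 19% / 36% |
| 6 | 7% / 16% | 8% / 17% |
| 12 | 0.1% / 0.5% | 0.2% / 0.4% |

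At 2 to 6 visits a year the range is therefore about 7–45%. By the dilution rule this leaves 55–93% of a true rate difference visible.

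**The case against.** The strongest reply is that the plan omits a rule but does not forbid a good one. The 12-month window governs who is immunocompromised; nothing says the transplant must be dated inside it, and data exist from December 2018. Annex 3 is an ICD-10 list for group membership, and Table 1 calls its contents the main diagnosis codes, so a dating list could exist elsewhere. Figure 1, which depicts the algorithm, could not be read and might hold a rule. All of this stands. It means that the strata are unspecified, and a reader who infers that they cannot be formed goes further than the documents do. It does not supply the missing rule: Annex 1, to which Table 1 points for the codes, lists no documents.

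A reader might also infer that most of the near stratum would be wrong. Requiring two coded visits of everyone in the same simulation does give 24–55% with dense early coding and 65–96% with a constant rate. But that leaves out entry on one inpatient claim, which the protocol allows and which matters most for recent recipients. Rule C alone keeps the share high at every visit rate, and the protocol does not call for it.

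The reach is limited as well. Section 8.7 lists bone marrow and organ transplant as whole groups, without the 100-day split, and section 8.5 calls the study mainly descriptive. Group membership, the overall incidence rate in the immunocompromised cohort and the exploratory effectiveness estimates do not depend on the split.

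**Conclusion.** The point holds as a gap in definition with a real but unknown effect. The split needs a transplant date, the listed codes do not supply one, and no readable section says how to derive it. The possible contamination runs from near 0% to more than 90%, depending on the dating rule, the visit rate and the true share of near recipients, none of which the documents give. The 7–45% range rests on the first-baseline-code rule, 2–6 coded visits a year, an even spread of transplants over 5–10 years, and a listed code on the transplant admission. At 12 visits a year it falls below 1%.

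The phrase *stratum nearest transplant* is a reading of intent. As written, section 8.2.1 places the first dose before the transplant, although the transplant code must already appear before the first dose. A transplant date is needed whichever direction is meant. The correction is worth making because it is cheap, but it concerns a subgroup split only.

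**What to change.** 1. Add transplant procedure codes (ICD-10-PCS and CPT-4) to Annex 3 for dating only, leaving group entry unchanged.
2. Define the transplant date as the latest such procedure before the index date in all data since 01 December 2018.
3. Form the 100-day strata only where a dated procedure determines the timing. Report recipients with status or complication codes alone as *transplant date not observed*.
4. Reconcile the text: state the direction of the interval between dose and transplant, assign day 100 (now in neither stratum), and say in both places of section 8.2.1 whether bone marrow recipients are included.

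The cost is a short code list and one more query on data the study already uses. The dated strata will be smaller. Because only 12 months of enrollment is required and data begin in December 2018, many older transplants will fall in the undated group, and the stratum beyond 100 days will hold only transplants seen within roughly two to two and a half years before index. The report should say so.
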